3.1	Study Objectives and Purpose	
Primary Study Objective Determine if the administration of G/P for 4 weeks beginning in the immediate peri-transplant period prevents establishment of HCV infection in HCV negative recipients receiving transplanted kidneys from HCV RNA positive donors
 
Secondary Objectives
 
 1. Evaluate the safety and tolerability of G/P in patients undergoing kidney transplantation by evaluating study-participation related (either related to G/P or HCV-viremia) severe and non-severe events from transplant until one-year post-transplant. Post-transplant allograft function outcomes: mean eGFR over time through the 1-year study period. We will also determine the rate of the following clinical outcomes related to safety: death, graft failure, acute allograft rejection, delayed graft function, ALT elevations > 5x ULN that occur within the 1-year study period 2. Capture patient reported outcomes 1 year after transplant or 1 year after consent (for those who remain on the waiting list) using the Functional Assessment of Chronic Illness Therapy Fatigue Subscale (FACIT-F) and compare results among patients who receive a kidney from a HCV-viremic donor and those who do not. 
Hypothesis We hypothesize that the administration of G/P (300mg/120mg) once daily for 4 weeks beginning within 24 hours of kidney transplant (either on-call to the operating room or within 24 hours of transplant) will prevent detectable HCV RNA in HCV RNA negative recipients receiving transplanted kidneys from HCV RNA positive donors during and after treatment completion.

AbbVie Investigator-Initiated Studies (IIS): Required Protocol Components

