3.2	Study Design	
This study is an open label, single-center, interventional, uncontrolled, pragmatic clinical trial for the donation of HCV positive kidneys to HCV negative patients with ESRD. It is a single arm study; all HCV-uninfected recipients of an HCV-viremic kidney transplant will begin G/P for 4 weeks beginning in the peri-transplant period (either on-call to the operating room or within 24 hours of transplant). Forty subjects will be enrolled (transplanted and dosed with G/P), with up to 80 total consented to determine eligibility. The target population is patients with ESRD who are at least 18 years old, do not have history of HCV infection, and are listed for transplant at the MGH Transplant Center.
 
Primary Endpoints SVR12 - sustained virologic response 12 weeks after completing G/P (16 weeks post-kidney transplant).
 
Secondary Endpoints
 
 • Severe and non-severe adverse events attributed to study drug • Severe and non-severe adverse events attributed to HCV-viremia • Assessment of HCV RNA viral load at on-treatment visits (week 2 and 4) • Post-transplant allograft function outcomes: mean eGFR over time through the 1-year study period. • The rate of the following clinical safety outcomes: death, graft failure, acute allograft rejection, delayed graft function, ALT elevations $> 5x$ ULN that occur within the 1-year study period. We will classify which of these events are related to G/P or HCV-Viremia and those which are not related.
3.3	Inclusion Criteria	
Donor Inclusion Criteria:
 
 a. Detectable HCV NAT test b. KDPI score is less than ≤ 0.850 c. Traditional Donor Selection Criteria Met - acceptable for transplantation per usual evaluation 
Recipient Inclusion Criteria:
 
 a. Met MGH Transplant Center criteria and already listed for kidney transplant with stage 5 CKD / ESRD (eGFR < 15 ml/min/1.73m² or on renal replacement therapy) b. Must agree to birth control. Women must agree to use birth control in accordance with Mycophenolate Risk Evaluation and Mitigation Strategy and at least one barrier method c. No evidence of clinically significant liver disease at the time of transplant readiness as determined by the clinical team d. Able to sign informed consent

AbbVie Investigator-Initiated Studies (IIS): Required Protocol Components

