3.6	Study Procedures	
The study will be a single-arm, open-label, pragmatic trial to evaluate the efficacy and safety of fixed-dose combination tablets of glecaprevir/pibrentasvir (G/P) for four weeks in HCV-negative subjects who consent to receive a kidney transplant from an HCV RNA-positive deceased kidney donor.
 
Patient reported outcomes will be performed 1 year after transplant or 1 year after consent for those who do not undergo transplant.
 
Screening Period
 
Potential subjects will be contacted by a member of the research staff to provide information about the study and to gauge interest. Interested individuals will be provided educational materials on HCV infection and transplantation. After this, potential subjects will be eligible for screening (there should be at least 24 hours between the educational visit and the screening visit, though special cases may allow these visits to occur on the same day as educational materials were provided). At the screening visit, the potential subject will review the informed consent again with the PI and sign if still interested in participating. Upon signing consent, the individual will receive a unique subject number. Both in-person and remote written informed consent will be conducted in accordance with institutional policy. Remote consent can be performed by a physician investigator in lieu of in person consent. During the consent process, the consenting physician will explain the scope of the study, potential risks and benefits. When the subject fully understands the scope of study participation, their consent will be obtained. Consents will be signed by the patient and mailed back to the study site, at which time the consenting physician will sign the consent. The rest of the screening visit will include a physical exam, vital signs, blood tests, and review of medical history and concomitant medications. The study investigators and research team will then review the potential subject's information to determine whether the patient is eligible to participate or not. Patients who are on contraindicated medications will need to be able to cease the contraindicated medication or switch to an alternative, allowed co-medication to be deemed eligible. Up to 80 subjects will be consented for trial participation, of whom 40 subjects will receive an HCV RNA-positive kidney and open-label G/P for 4 weeks post-transplant.
 
Waitlist Period
 
Subjects who have been enrolled in the study and are listed for kidney transplant at MGH Transplant Center will be placed in the waitlist group until being called for a transplant. While on the waitlist, subjects will be monitored by the transplant team for changes to health status, and changes in transplant waitlist status as per standard of care.
 
Baseline Period
 
Upon matching to a donor, the study subject will come into the hospital, following kidney transplantation standard-of-care procedures. The first dose of G/P will be given as early as "on call" to the operating room and no later than 24 hours after the transplant operation begins. The patient will be provided with a month supply of drug upon discharge from hospital. Treatment with G/P will then continue once daily for four weeks. Physical exam, vital signs, CMP, CBC & differential and pregnancy test will occur at baseline per standard of care.
 
On-treatment Period
 
Subjects will be followed per standard of care throughout the on-treatment period. Data will be recorded on day 1, week 2, and week 4 post-transplant: adverse events (including graft survival, mortality, allograft rejection, and potential hepatic and extrahepatic manifestations of HCV infection), concomitant medications, adherence to G/P dosing, vitals, physical exam, CMP, CBC & differential, HCV RNA will take place at these visits. Counseling regarding contraception and

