--	--

AbbVie Investigator-Initiated Studies (IIS): Required Protocol Components

		
Study records will be maintained at the study site for a minimum of 7 years after the study has completed (LSLV)

3.7	Statistical Analysis and Sample Size Justification	
Sample Size Justification
 
Power/Sample Size: This study is designed to generate preliminary data related to cure rates (defined as SVR12) from treating donor-derived HCV infection post kidney transplantation using 4 weeks of G/P. For this reason, the sample size was not determined with reference to power to detect differences between groups for the primary objective. The lower bound of a one-sided 95% confidence interval will be performed using the Clopper pearson exact method.
 
This is a pilot study with the goal to complete enrollment in 18 months. 40 patients will be dosed with medication. With 40 patients, if 40/40 are cured the lower bound of the confidence interval will be > 92%.
 
Statistical Analysis Plans
 
Include statistical methods for analysis of all primary and secondary endpoints
 
Variables/Time Points of Interest. The primary variable of interest will be HCV RNA at the multiple time-points assessed during and after treatment. The primary efficacy outcome “Prevention of HCV Transmission” will be determined by a negative HCV RNA test at 12 weeks after completing G/P. A summary of reasons for SVR12 non-response (e.g., establishment of infection, loss to follow-up, or other) will be provided. We will use an intention to treat analysis to determine, but will also modified intention to treat which only evaluates virologic failures. The safety outcomes include summation of treatment related-severe and non-severe adverse events. We will only collect data on adverse events deemed to be at possibly related to study participation (either from the study treatment G/P or from HCV viremia itself). An adverse event will be considered treatment-emergent if it begins or worsens in severity after initiation of study drug through 30 days post-study drug dosing. Related adverse events are those considered at least possibly related to study. The number and percentage of subjects with the following clinical outcomes and data post-transplant as applicable: death, graft failure, acute allograft rejection, delayed graft function, ALT elevations > 5x ULN, and SAEs. Statistical Methods Patient characteristics for this transplanted cohort (N=40) will be presented with summary statistics for baseline demographics and clinical variables. The SVR12 rate will be presented and 95% CI constructed with the exact test. Mean and standard deviation for on-treatment laboratory values will be presented to analyze safety.
 
Power/Sample Size: This study is designed to generate preliminary data related to cure rates (defined as SVR12) from treating donor-derived HCV infection post kidney transplantation using 4 weeks of G/P. For this reason, the sample size was not determined with reference to power to detect differences between groups for the primary objective. The lower bound of a one-sided 95% confidence interval will be performed using the Wilson’s score method.

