
AbbVie Investigator-Initiated Studies (IIS): Required Protocol Components

		
The primary efficacy endpoint is sustained virologic response 12 weeks post dosing (SVR12), defined as HCV RNA < LLOQ 12 weeks after the last actual dose of G/P. The SVR12 rate will be determined from all enrolled subjects who received an HCV RNA-positive kidney and received at least one dose of G/P study drug along with a two-sided 95% confidence interval. The confidence interval for the SVR 12 rate will be calculated using Clopper pearson exact method.
 
As an exploratory secondary outcome, we will compare FACIT-F scores among three groups 1. HCV-viremic donor kidney transplant recipients 2. Standard of care kidney transplant recipients 3. Patients remaining on the kidney transplant waiting list. Means will be compared using ANOVA testing.
 
Investigators will be responsible for analyzing data with statistical support.

3.8	Specific Drug Supply Requirements	
The investigator and research team will keep accurate records of the study drug (G/P 100 mg/40 mg). The study drug will be stored at 15° to 25°C (59° to 77°F) in the Clinical Trials Research Pharmacy (CTP) at MGH. It will be maintained under adequate security and stored under the conditions specified on the label until dispensed for subject use, destroyed on-site, or returned to AbbVie (or designee) as per ICH/GCP Guidelines, local regulations and MGH institutional policies.
 
The investigator and research team will also maintain a current disposition record of study drug (inventoried and dispensed) at the study site, including:
 
 • amount received and placed in storage area • amount currently in storage area • label identification number or batch number • amount dispensed to and returned by each subject, including unique subject identifiers • amount destroyed at study site, if applicable • amount returned to AbbVie, if applicable • dates and initials of person responsible for Investigational Product dispensing/accountability, as per the Delegation of Authority Form

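### Minor: the FACIT-F objective asks how viremic-kidney recipients compare with others, but the only stated method is a three-group ANOVA, which estimates neither comparison

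*Combined protocol and SAP*

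**What the plan says.** Section 3.1, secondary objective 2, is to collect FACIT-F at one year and "compare results among patients who receive a kidney from a HCV-viremic donor and those who do not".

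Section 3.7 introduces the analysis with "As an exploratory secondary outcome" and continues "we will compare FACIT-F scores among three groups": viremic-kidney recipients, standard-of-care recipients, and patients still on the waiting list. The only method given is "Means will be compared using ANOVA testing". For FACIT-F the document names no contrast, pairwise comparison, mean difference, confidence interval or multiplicity rule.

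Three other places bear on the point:
- Section 3.2, on numbers: "Forty subjects will be enrolled (transplanted and dosed with G/P), with up to 80 total consented to determine eligibility". Neither the sizes of the two comparator groups nor the source of the standard-of-care recipients is stated. FACIT-F is not in this section's list of secondary endpoints.
- Section 3.6, on timing: "Patient reported outcomes will be performed 1 year after transplant or 1 year after consent for those who do not undergo transplant". The flowchart in 3.5 shows no earlier assessment.
- Section 3.7, on sample size: "the sample size was not determined with reference to power to detect differences between groups for the primary objective". No SD, effect size or significance level is given for FACIT-F.

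**The concern.** The objective asks about one group against others. A three-group F test asks whether any of the three means differ. The two comparators differ from viremic-kidney recipients in different respects: standard-of-care recipients by type of donor, and waiting-list patients by having had no transplant. A significant F does not separate the two.

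If only the stated test is reported, the result is a p-value that may reflect transplant versus no transplant but could be read as bearing on viremic kidneys. A non-significant result would not show how large a difference remains compatible with the data. At stake is the interpretation of one patient-reported outcome, not the trial's efficacy conclusion.

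**Working it through.** The plan gives no figure for FACIT-F, so there is none to reproduce. The check asks how the stated test behaves when donor type makes no difference, and what an interval would show.

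**Inputs.** From the document: 40 viremic-kidney recipients, up to 80 consented (3.2), three groups, ANOVA (3.7). Assumed: two-sided 5% level; all comparators come from the 80 consented, so N = 80; splits (viremic/standard/waiting list) of 40/10/30, 40/20/20 and 40/30/10; effects in SD units.

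**1. Only the waiting list differs.** With means 0, 0 and −d (in SDs), the noncentrality is λ = Σ nᵢ(μᵢ − μ̄)² = d² × n_WL × (80 − n_WL)/80. The F test has 2 and 77 degrees of freedom and critical value 3.115.

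| Split | λ, d = 0.5 | P(reject) | λ, d = 0.8 | P(reject) |
|---|---|---|---|---|
| 40/10/30 | 0.25 × 30 × 50/80 = 4.69 | 46% | 0.64 × 30 × 50/80 = 12.0 | 87% |
| 40/20/20 | 0.25 × 20 × 60/80 = 3.75 | 38% | 0.64 × 20 × 60/80 = 9.6 | 78% |
| 40/30/10 | 0.25 × 10 × 70/80 = 2.19 | 24% | 0.64 × 10 × 70/80 = 5.6 | 54% |

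In every row viremic and standard-of-care recipients have the same mean, so a direct contrast between them rejects at its nominal 5%.

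**2. The comparators lie on either side.** Put standard-of-care recipients at +0.5 SD and the waiting list at −0.5 SD relative to viremic recipients, at 40/20/20. Then λ = 20 × 0.25 + 20 × 0.25 = 10 and the F test rejects 80% of the time, although viremic minus all others combined is zero.

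**3. Viremic recipients differ from both.** If they lie 0.5 SD below both other groups at 40/20/20, the F test has power 0.49, against 0.60 for the single contrast of viremic recipients with the rest.

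**4. Precision of the direct comparison.** With a pooled SD, the 95% half-width for viremic minus standard is t(0.975, 77) × √(1/40 + 1/n), with t = 1.991. The last column is the approximate Welch half-width if the SDs are in fact equal.

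| Standard recipients | √(1/40 + 1/n) | Pooled | Welch |
|---|---|---|---|
| 5 | 0.474 | 0.94 SD | 1.22 SD |
| 10 | 0.354 | 0.70 SD | 0.76 SD |
| 20 | 0.274 | 0.55 SD | 0.55 SD |

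**5. Unequal variances.** Simulated type I error of the classical F test at nominal 5%, under assumed SDs:

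| Split | SDs | Type I error |
|---|---|---|
| 40/10/30 | 9/13/12 | about 8% |
| 40/5/35 | 9/14/12 | about 10% |
| 40/10/30 | 9/9/12 | about 5% |
| 40/10/30 | 12/9/10 | about 3% |
| 40/10/30 | 13/9/12 | about 3% |

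The direction depends on whether the largest group has the smallest or the largest SD, and the document does not say.

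**The case against.** The strongest reply is that little hangs on this. Section 3.7 calls the comparison exploratory, section 3.2 does not list FACIT-F among the secondary endpoints, and the trial is a pilot that was not sized for group differences. That stands, and it is why the point is minor.

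A second reply is that the plan does not confine itself to an omnibus test. Follow-up comparisons after ANOVA are routine, the group means would presumably be shown, and splitting the non-recipients in two is what makes it possible to separate donor type from transplantation. This also stands in part: the text is under-specified rather than committed to a lone F test. But no follow-up comparison is written down, and three unadjusted comparisons chosen later carry about a 14% chance of at least one false positive (1 − 0.95³ = 0.143, treating them as independent).

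Two stronger readings are tempting, and the document supports neither:
- A reader might infer that the group sizes are bound to be unequal, with 40 viremic recipients and at most 40 others split in two. That holds only if every comparator comes from the 80 consented. Section 3.7 does not say where the standard-of-care recipients come from.
- A reader might infer that classical ANOVA would exceed its 5% error rate. Under assumed SDs the rate runs from about 3% to about 10%, so it may fall on either side. This is not a shown error.

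**Conclusion.** The concern holds as a minor point. The objective asks for a comparison of viremic-kidney recipients with others. The stated test estimates neither relevant difference and can be significant with no difference by donor type: 24% to 46% of the time for a waiting list 0.5 SD lower, and 54% to 87% for 0.8 SD. These figures rest on the assumed splits, effects and N = 80; none comes from the document. The direct comparison would be imprecise on any of the splits examined, which is a reason to report an interval rather than a p-value alone. The SVR12 and safety conclusions are unaffected.

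Named contrasts would make the reported quantity match the question, but they would not isolate an effect of viremic kidneys. The groups are not randomised, there is no baseline FACIT-F, and the year is counted from transplant for some patients and from consent for others.

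**What to change.** In section 3.7, replace the ANOVA sentence with two prespecified mean differences in FACIT-F, each with a 95% confidence interval:
1. viremic-kidney versus standard-of-care recipients;
2. viremic-kidney recipients versus waiting-list patients.

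Report the size of each group, and label both comparisons exploratory and unadjusted for multiplicity. An unequal-variance (Welch) interval is a reasonable default because the group sizes may differ; it will be wider than the pooled interval when a group is very small. Reword objective 2 in section 3.1 to name the same two comparisons, and state the limits on interpretation given in the verdict.

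The cost is a few sentences in 3.7 and one in 3.1. No new data, visits or subjects are needed.

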
SAEs will be categorized as pre-transplant or post-transplant, and pre-treatment, on-treatment, or post-treatment. The following information will be reported to the sponsor and to the IRB:

- Admission and discharge notes
- Consults with vitals and physical exam, as available
- All labs
- Imaging and procedure reports
- Medication administration record

All SAE correspondence with AbbVie will be sent to: [contact]

For events that meet the IND safety reporting criteria, the investigator will also copy AbbVie on submission of SAE report to FDA.

Adverse event severity

Per investigator, adverse events will be coded using the Medical Dictionary for Regulatory Activities (MedDRA) using the following definitions:

1. **Mild:** Adverse events and/or symptoms recorded in the medical record where no therapy was given to treat the event or where an over-the-counter medication/intervention ONLY was given to treat the event.
2. **Moderate:** Adverse events and/or symptoms recorded in the medical record requiring prescription medication treatment.
3. **Severe:** Adverse events and/or symptoms requiring any study drug discontinuation will be defined and coded as severe. ANEMIA events requiring blood transfusion will be coded as severe.

Adverse event relatedness to study drug

Per investigator, adverse events will be assessed for relatedness to study drug according to the following definitions:

- **Reasonable possibility (“associated”):** An adverse event where there is evidence to suggest a causal relationship between the study drug and the adverse event
- **No reasonable possibility (“not associated”):** An adverse event where there is no evidence to suggest a causal relationship between the study drug and the adverse event.

Pregnancy

AbbVie Investigator-Initiated Studies (IIS): Required Protocol Components

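### Adverse event severity is graded by action taken, so once G/P ends at week 4 transfused anemia is the only listed route to Severe, although severe events are evaluated to one year

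*Combined protocol and SAP*

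**What the plan says.** Section 3.9 (Adverse event severity) sets three grades, each defined by the response to the event.

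- **Mild:** no treatment, or over-the-counter measures only.
- **Moderate:** "Adverse events and/or symptoms recorded in the medical record requiring prescription medication treatment".
- **Severe:** "Adverse events and/or symptoms requiring any study drug discontinuation will be defined and coded as severe", and in addition "ANEMIA events requiring blood transfusion will be coded as severe".

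The protocol gives no other criterion for Severe.

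On exposure, section 3.6 (Baseline Period) states: "Treatment with G/P will then continue once daily for four weeks". Section 3.6 (Subject Withdrawal Criteria) places any retreatment after failure outside the protocol.

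On the evaluation period, secondary objective 1 in section 3.1 covers participation-related "severe and non-severe events from transplant until one-year post-transplant". Section 3.2 makes the severe/non-severe split a secondary endpoint twice, once for events attributed to study drug and once as "Severe and non-severe adverse events attributed to HCV-viremia". Neither bullet states a window. Section 3.6 (Follow-up Period) records adverse events up to week 52 after transplant.

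**The concern.** A severity grade should describe how intense an event was. Here the top grade is tied mainly to an action that is possible only while G/P is being taken. Once the course ends, an event of any intensity other than transfused anemia can be graded Moderate at most.

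The error also runs the other way: a low-intensity event that requires G/P to be stopped is Severe. The split therefore partly measures whether the subject was on drug.

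The viremia endpoint is the more exposed of the two, because viremia from a relapse after the four-week course appears off drug. A low count of severe viremia-attributed events would then partly reflect the definition and could be read as reassurance about safety.

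**Working it through.** The plan gives no figure for this point. The check sets the definitions against the dosing and evaluation periods.

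**Step 1. Is the discontinuation route open after week 4?** G/P is the only study drug and lasts four weeks (3.6). The ALT rule in section 3.9 (Toxicity) that can lead to discontinuation applies only during treatment. Stopping a retreatment regimen is not stopping study drug, because retreatment is outside the protocol (3.6). The route is therefore closed after week 4, or earlier in a subject who has already stopped permanently. Transfused anemia carries no time limit and remains.

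**Step 2. How much of the evaluation period is affected?**

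| Basis | Source | Off drug | Share |
|---|---|---|---|
| Calendar time, transplant to one year | 3.1, 3.6 | 52 − 4 = 48 of 52 weeks | 48/52 = 92.3% |
| Treatment-emergent window: 28 days of dosing plus 30 days | 3.7 | 30 of 58 days | 30/58 = 51.7% |
| Scheduled recording points in the text | 3.6 | 3 of 6 | 50% |
| Scheduled adverse event rows in the flowchart | 3.5 | 3 of 8 | 37.5% |

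The six points in the text are days 1, 14 and 28 on drug, then days 28 + 28 = 56, 28 + 84 = 112 and 52 × 7 = 364 off drug. The eight flowchart rows are peri-transplant, day 1, week 2, week 4, end of G/P, and post-treatment week 4, week 12 and 1 year. The event-driven rows (treatment failure and premature discontinuation) are left out. All four shares describe time or visits, not events.

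**Step 3. Does one event get two grades?** Take a confirmed ALT above 8 times ULN with no alternate etiology.

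- On drug, section 3.9 (Toxicity) leads to discontinuation, so the grade is Severe.
- Off drug, the grade is Moderate if prescription medication is required and Mild if no therapy is given.

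**Step 4. Is the event caught elsewhere?** The ALT example is, because ALT above 5 times ULN is a separate outcome in sections 3.2 and 3.7. Not every event is. Section 2.1 names cytomegalovirus infection among the complications reported when antiviral treatment was delayed. Such an infection, if attributed to viremia, arising off drug and treated by prescription without admission, could be Moderate at most. It is not on the list of separate outcomes in section 3.2 and need not meet an SAE criterion.

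**Step 5. Are the three grades exhaustive?** No. An event managed only by a procedure, other than anemia by transfusion, fits none of them unless study drug was stopped.

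**The case against.** The strongest reply is that little is lost.

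- **Separate capture.** Death, graft failure, rejection, delayed graft function and marked ALT elevation are counted on their own, and section 3.2 adds: "We will classify which of these events are related to G/P or HCV-Viremia and those which are not related". SAEs are tabulated (3.7), and section 3.9 says "SAEs will be categorized as pre-transplant or post-transplant, and pre-treatment, on-treatment, or post-treatment". The SAE criteria include hospitalization and important medical events as judged by the investigator. This stands: grave late events remain visible. It does not repair the two endpoints, because seriousness is nowhere mapped to the severity grade.
- **The 30-day window.** Section 3.7 defines treatment-emergent events up to 30 days after dosing. If that governs the drug-attributed summary, the off-drug share is 52%, not 92%. This is a possible reading, but section 3.7 does not tie the window to these endpoints, and more than half of even that window is off drug.
- **Time is not events.** Only related events are reported, and late viremia-related events would be expected mainly after virologic failure, which the hypothesis in section 3.1 expects not to occur. This stands: 92% must not be read as a proportion of events misgraded.
- **Pragmatic grading.** Grading by action suits a trial followed per standard of care, and a smaller remedy is possible: reporting the split by treatment period. That would expose the dependence on drug status but would not remove it.
- **Investigator judgment.** The grading is introduced as the investigator's, but coding must follow the listed definitions, which do not clearly allow another route to Severe.

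**Conclusion.** The concern holds. The grading rule in section 3.9 does not fit the one-year evaluation in section 3.1. Followed as written, it misgrades off-drug events in two named secondary endpoints.

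For 48 of 52 weeks, transfused anemia is the only listed route to Severe. This assumes the section 3.1 window and a full four-week course. The number of events affected is unknown, because the documents give no event data.

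The consequence is limited. Both endpoints are descriptive, and no stated test or stopping rule uses the grade. The events most affected are related events of severe intensity that are neither SAEs nor among the outcomes listed separately in section 3.2. The point should be fixed. Confidence in the contradiction is high; its practical effect may be small.

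**What to change.** Make four linked changes in one amendment.

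1. In section 3.9, define Severe by clinical intensity independent of study-drug status, for example grade 3 or higher on a standard toxicity scale or an equivalent intensity definition.
2. Record whether the event led to G/P discontinuation as a separate flag in the adverse event log.
3. Apply the new grade through week 52 to both severe/non-severe endpoints, and state that window in the two bullets in section 3.2.
4. In section 3.7, say how the 30-day treatment-emergent definition relates to these endpoints.

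This alters grading only and leaves every treatment-stopping rule untouched. It needs no extra visits. Events already logged must be regraded from the medical record, open label, and for some the record may hold only the action taken. More events may be reported as severe.
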